### Randomization

Table 1. Randomization and Stratification of Mothers

Gestational Age	Group 1 Early Expressers	Group 2 Intermediate Expressers	Group 3 Late Expressers
23-27 weeks	0-60 minutes	61-180 minutes	181-360 minutes
28-32 weeks	0-60 minutes	61-180 minutes	181-360 minutes

mothers into groups. Following the birth of an infant weighing less than 1500 grams, with a gestational age between 23-32 weeks, mothers who continue to meet inclusion criteria will be stratified according to the gestational age of the infant (23-27 weeks and 28-32 weeks). Gestational age will be determined through one of the following; 1st or 2nd trimester ultrasound or the average of the obstetric gestational age and the results of the Ballard exam. This stratification is based upon likely differences in breast milk production in mothers who deliver earlier in gestation due to decreased mammary gland development and decreased levels of prenatal hormones necessary for preparation of the breast for lactation.

Following stratification, mothers will be randomly assigned to one of three groups to begin milk expression at different time periods following delivery. Group 1 (early expressers) will begin milk expression 0-60 minutes following delivery, Group II (intermediate expressers) will begin 61-180 minutes following delivery, and Group III (late expressers) will begin 181-360 minutes following delivery. The selection of the time periods for the groups is based upon our preliminary data showing greater milk volume and earlier lactogenesis stage II in women who began milk expression within 1 hour following delivery compared to those who began milk expression 1-6 hours following delivery (Parker et al., in press).

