### **Exploratory Aim 2**

Exploratory Aim 2 is to examine the effect of timing of initiation of breast milk expression on milk volume and lactogenesis stage II in mothers who deliver at an earlier gestation (23-27 weeks) and those who delivery at a later gestation (28-32 weeks). Information will be collected according to the procedure in Aim 1.

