### **Analyses for Aim 1**

The primary efficacy outcomes are amounts of breast milk expressed over the first 7 days post-initiation; days 14, 21, 28, 35, and 42 days post-initiation and weekly, and number of days to achieve lactogenesis stage II. To examine expressed breast milk amount over time (i.e. production of breast milk immediately after initiation and subsequently, volume measured daily over the first 7 days and on days 14, 21, 28, 28, and 42 post-initiation and weekly), we will compare the longitudinal profile of milk volume expressed in the three groups over the

study period using mixed effects models (MEM) analyses. These analyses will estimate the average change in breast milk volume within each group (early vs. immediate vs. late initiation) and individual change in breast milk volume for each mother. MEM analyses allow for missing data, measurement of study subjects at different time points during the study, and time varying covariates. MEM can also take into account the effect of clustering, i.e. correlation of repeated breast milk measurements within one subject (Hedeker & Gibbons, 2006; McCulloch & Searle, 2001). The efficacy variable expressed breast milk volume (mL) will be used as the dependent variable with treatment status (early vs. intermediate vs. late initiation), time and time-by-treatment interaction and gestational group (23-27 weeks vs. 38-32 weeks) as primary independent variables. In a second step, additional covariates will be included in the models to adjust for putative predictive variables such as age, mother's weight at delivery, diagnosis of preeclampsia or diabetes, parity, birth weight, weeks of gestation, behavioral factors including skin-to-skin contact ("kangaroo care"), lactation support and mean number of pumping attempts per day. Effect modifications of covariates will be examined through inclusion of a covariate-by-treatment interaction term in the multivariable models. For example, a significant age-by-treatment interaction would suggest that the relationship between treatment and milk volume is different for older mothers compared to younger mothers. Potential key intervening variables such as behavioral factors will be further examined using mediation analysis. Further, the relationship of maternal mood with amount of breast milk will be examined by inclusion of the MAACL-R scores obtained at discharge, days 21 and 42 in the longitudinal MEM model.

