Additionally, unadjusted mean differences in volume of breast milk at day 1 through 42 will first be compared overall via one-way ANOVA (or equivalently non-parametric Kruskal-Wallis tests) between the three groups. Subsequently, pooled t-tests will be used to compare unadjusted means pairwise between the groups (using significance level  $\alpha = 0.02$  to account for multiple comparisons). Mean differences for volume of breast milk at day 1 through 42 and number of days to achieve lactogenesis stage II will be adjusted for gestational group (strata) and putative covariates such as age, mother's weight at delivery, diagnosis of preeclampsia or diabetes, parity, birth weight, weeks of gestation, behavioral factors including kangaroo care and lactation support. Mean number of pumping attempts per day will be compared for each outcome measure (as dependent variable) using a general linear model (GLM) approach for the three milk initiation groups.

Furthermore, survival distribution for time from delivery to lactogenesis stage II will be obtained for each group using the Kaplan-Meier product limit method, and will be compared using the logrank test. Cox proportional hazards regression modeling (PHM) will be used with time from delivery to lactogenesis stage II as the dependent variable, and treatment (early vs. moderate vs. late initiation) and gestational group (strata) as the primary independent variables. Additional covariates and interaction terms will be added as described above for MEM analyses.

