### **Analyses for Exploratory Aims**

Aim 1. Volume of breast milk at discharge will be compared via one-way ANOVA; weekly percentage of breast milk during hospitalization will be compared between the three groups using chi-square tests.

Aim 2. In a first step, unadjusted mean time to lactogenesis stage II and mean volume of breast milk over the first 6 weeks (days 1 through 42) will be compared between the four groups: early timing of initiation of expression (TIE) / 23-27 weeks of gestation, late TIE / 23-27 weeks of gestation, early TIE / 28-32 weeks of gestation, and late TIE / 28-32 weeks of gestation, using one-way ANOVA. Subsequently, post hoc pooled t-tests (Tukey's) will be used to compare time to lactogenesis stage II and volume of breast milk means pairwise for the two early and the two late TIE groups between the two degrees of prematurity (23-27 vs. 28-32 weeks) and for the early-late TIE groups within each degree of prematurity. Adjusted means will be obtained and compared between the groups using a general linear models (GLM) approach with gestational age/degree of prematurity group as the primary independent variable and time to lactogenesis stage II (or amount of breast milk expressed at days 1-7) as the dependent variable. Additional covariates will be included in the models to adjust for putative predictive variables as described above.

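### Minor: the Exploratory Aim 2 analysis names no timing-by-gestational-stratum contrast, so within it a difference in timing effect between strata could only be inferred from two separate tests

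*Combined protocol and SAP*

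**What the plan says.** The Exploratory Aim 2 section asks about the effect of timing on two outcomes, lactogenesis stage II and milk volume. It describes the mothers concerned in these words: "in mothers who deliver at an earlier gestation (23-27 weeks) and those who delivery at a later gestation (28-32 weeks".

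The analysis, under Analyses for Exploratory Aims (Aim 2), has three steps:

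1. Unadjusted means "will be compared between the four groups: early timing of initiation of expression (TIE) / 23-27 weeks of gestation", plus late/23-27, early/28-32 and late/28-32 weeks, by one-way ANOVA. The intermediate arm is not among the four cells.
2. Tukey post hoc tests of two kinds. One kind compares strata with timing held fixed: "pairwise for the two early and the two late TIE groups between the two degrees of prematurity". The other kind compares timing with stratum held fixed: "for the early-late TIE groups within each degree of prematurity".
3. A general linear model "with gestational age/degree of prematurity group as the primary independent variable", with covariates added as for Aim 1.

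Two other places bear on the point. The Randomization section gives the reason for the strata: "This stratification is based upon likely differences in breast milk production in mothers who deliver earlier in gestation". Analyses for Aim 1 contains a general clause: "Effect modifications of covariates will be examined through inclusion of a covariate-by-treatment interaction term in the multivariable models". Weeks of gestation is one of the covariates listed there. For the Cox model of time to lactogenesis stage II, the same section adds: "Additional covariates and interaction terms will be added as described above for MEM analyses".

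**The concern.** None of the three steps estimates the quantity that would show timing working differently by gestation, namely (early minus late at 23-27 weeks) minus (early minus late at 28-32 weeks).

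- The ANOVA pools timing and gestation into one four-cell factor. The Randomization section expects gestation to matter, so a significant result need not involve timing.
- The cross-stratum Tukey tests measure gestation with timing held fixed.
- The within-stratum Tukey tests measure timing, one stratum at a time.
- The linear model names gestational group as its leading factor. It names neither timing nor an interaction.

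A reader of the Aim 2 results who wants to know whether the timing effect differs can only set the two within-stratum results side by side. If one is significant and the other is not, the natural conclusion is that timing matters in one gestational group only. That pattern is common when the effect is identical in both.

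**Working it through.** **Inputs from the documents** (Sample Size Determination / Power Analysis): 60 mothers per arm, SD 55.0 h for time to lactogenesis stage II, detectable difference 34.1 h, two-sided alpha 0.02, power 85%.

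**Assumptions.** Stratum sizes are not given, so I take 30/30 or 20/40 mothers per arm by stratum. The Aim 2 text states no alpha, so I show both 0.05 and the 0.02 used elsewhere in the plan.

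**1. The plan's own figure.** 34.1/55.0 = 0.62 SD. With 60 per arm, 0.62/√(2/60) = 3.40. The normal approximation gives Φ(3.40 − 2.33), or 85.8%, and the exact noncentral t gives 84.9%. The stated 85% reproduces. No power is stated for Aim 2.

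**2. The four-cell ANOVA when only gestation matters.** With no timing effect and a gestation gap of 0.5 SD, the noncentrality λ = Σ n(mean − grand mean)² is:
- 30/30: 4 × 30 × 0.25² = 7.5.
- 20/40: 2 × 20 × (0.333)² + 2 × 40 × (0.167)² = 6.67.

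From the noncentral F(3, 116), the ANOVA rejects in 61% and 55% of trials at 0.05, and in 46% and 40% at 0.02. At 0.05, a 0.3 SD gap gives 24% and 22%, and a 0.7 SD gap gives 90% and 86%.

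**3. The within-stratum tests when timing works equally in both strata.** The Tukey critical value at 0.05 for four cells and 116 df is q/√2 = 2.61. For a 0.62 SD effect the noncentrality is 0.62/√(2/n):

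| Mothers per cell | Noncentrality | Power of the early-late Tukey test (0.05) |
|---|---|---|
| 20 | 1.96 | 26% |
| 30 | 2.40 | 42% |
| 40 | 2.77 | 57% |

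Treating the two tests as independent, the chance that exactly one is significant is p₁(1 − p₂) + p₂(1 − p₁):
- 30/30: 2 × 0.422 × 0.578 = 49%.
- 20/40: 0.264 × 0.433 + 0.567 × 0.736 = 53%.

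The tests share one error variance, which lowers this slightly. Simulation of 40,000 trials per layout gives:

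| Common timing effect | Alpha | Exactly one stratum significant (range over 30/30 and 20/40) |
|---|---|---|
| 0 | 0.05 | 2% |
| 0.3 SD | 0.05 | 14-15% |
| 0.62 SD | 0.05 | 48-52% |
| 1.0 SD | 0.05 | 19-30% |
| 0.62 SD | 0.02 | 41-45% |

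The interaction test rejects in about 5% of the same trials at 0.05, and about 2% at 0.02.

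**4. What a direct contrast could detect.** For early versus late, the standard error of the difference in timing effects is SD × √(2/n_A + 2/n_B). With 30 per cell this is 0.365 SD. A true difference of 0.62 SD gives 0.62/0.365 = 1.70, or about 26% power at alpha 0.02. The difference detectable with 85% power is 0.365 × (2.326 + 1.036) = 1.23 SD, which is 67.5 h. At 20/40 the power is about 23%. At a more uneven 15/45 it is about 19%, with a detectable difference of 1.42 SD (78 h).

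**The case against.** **The plan already has an interaction route.** A reader might infer that it has none. The documents do not support that: the covariate-by-treatment clause in Analyses for Aim 1 covers weeks of gestation, and interaction terms are extended to the Cox model. Read plainly, that could give a gestation-by-timing term for both Aim 2 outcomes. This stands as a limit on the point, but it does not remove it. The clause is generic and treats weeks of gestation as one of many unranked covariates. It does not use the two randomization strata. In the Aim 1 mixed model, gestational group enters as a primary variable, and the only interaction named there is time-by-treatment. The Aim 2 text carries over additional covariates but, unlike the Cox paragraph, not interaction terms.

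**The aim may want only stratum-specific effects.** Its wording can be read that way, and the within-stratum tests then answer it. Nothing in the documents says a difference will be claimed from discordant p-values. This also stands. Still, the planned cross-stratum comparisons and the reason for stratifying point to an interest in comparing strata, and the results will be read side by side in any case.

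**The ANOVA is only a first step.** A reader might infer that it will produce false timing claims. It should not: it is an omnibus test, and the Tukey step separates timing from gestation. With no timing effect, each within-stratum test rejects only about 1% of the time at a family level of 0.05. The 55-61% in step 2 is the ANOVA correctly finding that cells differ. The fair criticism is only that it does not inform on timing.

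**The disagreement rate depends on the assumed effect.** It does. The plan's 0.62 SD lies near the peak, which is why the other effect sizes are shown.

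**Conclusion.** The point holds for the Exploratory Aim 2 analysis as written: it contains no timing-by-stratum contrast, and it leaves out the intermediate arm. If the timing effect were the same 0.62 SD in both strata, about half of trials would show significance in one stratum only (48-52% at 0.05, 41-45% at 0.02). With smaller or larger common effects at 0.05 this is much less frequent. These figures rest on assumed stratum sizes of 30/30 or 20/40 per arm and on equal variances.

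It would go too far to say that the plan cannot examine effect modification by gestation at all, or that it commits to a false subgroup claim. The severity is minor: the aim is exploratory, carries no power claim or decision rule, and affects no primary conclusion.

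**What to change.** In Analyses for Exploratory Aims (Aim 2):

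- Replace the one-way ANOVA with a model containing timing (all three arms), gestational stratum and timing-by-stratum for each outcome. Put the same interaction in the mixed model for milk volume and the Cox model for lactogenesis stage II.
- Take the within-stratum timing effects from that model.
- Report the interaction with its confidence interval, labelled exploratory.
- State that a difference between strata will be claimed only from the interaction term.

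The cost is a wording change and the added interaction term, with no new data or mothers. The downside is low power (step 4 of the working). The interaction will often be inconclusive, so the confidence interval should carry the message rather than the p-value.

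### The adjusted model for Exploratory Aim 2 tests gestational group while also adjusting for weeks of gestation, so its between-stratum contrast measures only a jump at 28 weeks

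*Combined protocol and SAP*

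**What the plan says.** The Aim 2 paragraph of Analyses for Exploratory Aims has two steps. The first is unadjusted: a one-way ANOVA over four groups (early or late initiation by earlier or later gestation), followed by Tukey comparisons between the two degrees of prematurity and between early and late initiation within each. The second obtains adjusted means from a general linear model with "gestational age/degree of prematurity group as the primary independent variable". It closes with "Additional covariates will be included in the models to adjust for putative predictive variables as described above".

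The lists referred to are in Analyses for Aim 1. The mixed-model list includes "parity, birth weight, weeks of gestation, behavioral factors including skin-to-skin contact", and the list for the adjusted mean differences includes "parity, birth weight, weeks of gestation, behavioral factors including kangaroo care and lactation support". Both name weeks of gestation and birth weight. Nothing exempts either variable from the Aim 2 model.

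The Randomization section forms the two groups by dividing gestational age into 23-27 and 28-32 weeks. It justifies this by expecting differences in milk production with earlier delivery, through less mammary development and lower hormone levels. It claims no threshold at 28 weeks.

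**The concern.** Gestational group is a coarse version of weeks of gestation. With both in one model, the group coefficient compares the two strata at the same number of weeks. No mother at 25 weeks has a counterpart at 25 weeks in the later stratum, so the coefficient can pick up only a discontinuity at 28 weeks. That is not the difference between the two degrees of prematurity.

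At stake is the interpretation of the adjusted contrast. An unadjusted difference between strata that shrinks or vanishes on adjustment could be read as evidence that degree of prematurity does not matter for milk volume or lactogenesis II. The shrinkage would come from the model specification.

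**Working it through.** **Nearest stated figure.** The documents give no power or precision for Exploratory Aim 2. The nearest figure, in Sample Size Determination / Power Analysis, is 85% power for 34.1 hours to lactogenesis II with SD 55.0, 60 per group and two-sided alpha 0.02. The standard error is 55.0 × √(2/60) = 10.04, and 34.1/10.04 = 3.396. Subtracting 2.326 leaves 1.070, which gives 85.8% (84.9% by noncentral t). The figure reproduces; the point does not depend on it.

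**Inputs.** From the documents: weeks 23-32, groups cut at 28, 180 mothers. Assumed: the distribution of weeks. Three were tried: uniform, rising towards 32 weeks, and roughly normal around 28. Birth weight was assumed to rise 150 g per week with SD 200 g.

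**Overlap of group and weeks, uniform case.** The stratum means are 25 and 30 weeks, 5 weeks apart. The SD of weeks is √(99/12) = 2.872, and the SD of a 50:50 indicator is 0.5.

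- Covariance = 0.5 × 0.5 × 5 = 1.25
- r = 1.25/(0.5 × 2.872) = 0.870
- Variance inflation factor (VIF) = 1/(1 − r²) = 1/(1 − 0.7576) = 4.125, so the standard error is multiplied by √4.125 = 2.03

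For the rising distribution r = 0.833 and VIF = 3.27; for the normal one r = 0.817 and VIF = 3.01.

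**What the group coefficient estimates.** Let the mean outcome be a + s × weeks + δ × group. Without weeks, the group coefficient is δ + s × (difference in mean weeks). With weeks, it is δ alone. A 50-unit stratum difference was simulated in a large sample under the three distributions:

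| Source of the 50 units | Group only | Plus weeks | Plus birth weight only |
|---|---|---|---|
| Linear in weeks | 50 | about 0 | 24-26 |
| Half linear, half step at 28 | 50 | about 25 | 36-38 |
| All step at 28 | 50 | 50 | 49-50 |

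Adding birth weight to a model that already has weeks changed nothing. With birth weight alone the VIF was 2.0-2.7.

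**At the trial's size.** In 2,000 simulated trials of 180 mothers (uniform weeks, linear gradient, residual SD 100), the mean group estimate was 50.1 (SD 14.9) without weeks and −0.1 (SD 31.4) with weeks. The estimated timing effect was 50.1 in both models.

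**Cost when the estimate is unbiased.** Take a pure step of 0.62 SD, 90 mothers per stratum and alpha 0.02 (the plan's level for primary outcomes, assumed here).

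- Group only: 0.62/√(2/90) = 4.159, less 2.326 = 1.833, power 97%
- VIF 3: 4.159/√3 = 2.401, less 2.326 = 0.075, power 53%
- VIF 4.1: 4.159/√4.1 = 2.054, less 2.326 = −0.272, power 39%

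The equal split is a simplification for the VIF of 3, which came from a distribution with 59% of mothers in the later stratum.

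**Timing within strata.** With a true early-late effect of 0.50 and a timing-by-stratum interaction of 0.30 (uniform weeks, linear gradient), the estimates were 0.50 and 0.30 both with and without weeks, and the standard errors did not change (0.21 and 0.30). Those standard errors match 45 mothers per cell: √(2/45) = 0.21 and √(4/45) = 0.30. With three arms of 60 and equal strata there would be 30 per cell, giving √(2/30) = 0.26 and √(4/30) = 0.37. Randomization within strata keeps timing unrelated to weeks, so the conclusion is the same.

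**The case against.** **The aim is about timing.** The section headed Exploratory Aim 2 asks for the effect of timing of initiation in mothers delivering earlier and in those delivering later. A reader might infer that the adjusted model destroys the aim's estimand, or that adding weeks biases the timing effects in Aim 1. The documents support neither. The timing contrasts survive the adjustment, and only the between-stratum contrast is damaged. The analysis paragraph nevertheless makes that contrast primary in the adjusted model. The same sentence names no timing term or timing-by-gestation interaction; that is a separate gap, which the change below does not close.

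**The lists are examples.** Both are worded as illustrations of the covariates that might be used, so an analyst could omit weeks. This stands as a reason not to call the double entry mandatory. Still, both lists name the variable, and the Aim 2 paragraph imports them without exception.

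**The unadjusted difference is still reported.** The ANOVA and Tukey comparisons estimate the gestational difference without weeks. So it would be wrong to infer that the trial must report no gestational difference. The risk is a misleading contrast between the two steps.

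**The gradient may not be linear.** Full removal needs a roughly linear gradient. The rationale in Randomization fits a gradient but does not establish one. Under a pure step the harm is lost precision only.

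**Birth weight is not the same quantity as gestation.** This stands. Under the assumed values it absorbs about half of a linear gradient. Applying the 1500 g ceiling (with an assumed mean of 1000-1200 g at 28 weeks) leaves 51-56% of the difference and lowers the VIF for weeks from 4.1 to 3.2-3.7. Whether to adjust for birth weight is largely a modelling choice.

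**Conclusion.** The point holds for the adjusted between-stratum contrast. Followed as written, the Aim 2 model contains both gestational group and the variable that defines it, so the group coefficient is a jump at 28 weeks. Under a roughly linear gradient the adjusted difference goes to about zero; if half of it is a step, about half remains; if all of it is a step, it is unbiased with about 3 to 4 times the variance. These sizes depend on assumed distributions of weeks. That the coefficient changes meaning does not.

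The reach is limited. The timing effects in Aim 1, the early-late contrasts within strata and the unadjusted Aim 2 comparisons are untouched, and the analysis is exploratory with no stated power. It should be corrected because the error is avoidable and would mislead on the very difference given as the reason for stratifying.

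**What to change.** In the Aim 2 paragraph of Analyses for Exploratory Aims, state that weeks of gestation is excluded from the adjusted model whenever gestational group is a term. If a continuous analysis is wanted, fit a separate model with weeks in place of the group. Leave birth weight out of the main adjusted between-stratum comparison, or add it only as a labelled sensitivity analysis.

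The change takes a sentence or two and needs no new data or change in sample size. The small downside is less adjustment for birth weight in that one contrast.
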